14.2.18.2.1.1 to 14.2.18.2.1.2	(EO1) Exploratory analyses:6-Minute Walk distance - Random Slope Analysis Separately for each stratum - Raw values at each visit - Pirfenidone or Nintedanib
14.2.18.2.2.1 to 14.2.18.2.2.2	(EO1) Exploratory analyses:6-Minute Walk distance - Random Slope Analysis Separately for each stratum - Change from baseline at each visit - Pirfenidone or Nintedanib
14.2.18.2.3.1.a to 14.2.18.2.3.2.a	(EO1) Exploratory analyses:6-Minute Walk distance - Random Slope Analysis Separately for each stratum - Anova table - Pirfenidone or Nintedanib
14.2.18.2.3.1.b to 14.2.18.2.3.2.b	(EO1) Exploratory analyses:6-Minute Walk distance - Random Slope Analysis Separately for each stratum - Model parameter estimates - Pirfenidone or Nintedanib
14.2.18.2.3.1.c to 14.2.18.2.3.2.c	(EO1) Exploratory analyses:6-Minute Walk distance - Random Slope Analysis Separately for each stratum - Least Square Means at each visit- Pirfenidone or Nintedanib

14.2.18.2.3.1.d to 14.2.18.2.3.2.d	(EO1) Exploratory analyses:6-Minute Walk distance - Random Slope Analysis Separately for each stratum - Least Square Means for change from baseline at each visit - Pirfenidone or Nintedanib
14.2.19.1.1.1 to 14.2.19.1.1.2	(EO2) Exploratory analyses: HRCT image analysis (total lung volume) - SVC breathhold at CT scanning $\geq 90\%$ of SVC supine - raw value at each visit
14.2.19.1.2.1.b to 14.2.19.1.2.2	(EO2) Exploratory analyses: HRCT image analysis (total lung volume) - SVC breathhold at CT scanning $\geq 90\%$ of SVC supine - change from baseline
14.2.19.1.3.1.a to 14.2.19.1.3.2.a	(EO2) Exploratory analyses: HRCT image analysis (total lung volume) - SVC breathhold at CT scanning $\geq 90\%$ of SVC supine - Anova table
14.2.19.1.3.1.b to 14.2.19.1.3.2.b	(EO2) Exploratory analyses: HRCT image analysis (total lung volume) - SVC breathhold at CT scanning $\geq 90\%$ of SVC supine - Model parameter estimates
14.2.19.1.3.1.c to 14.2.19.1.3.2.c	(EO2) Exploratory analyses: HRCT image analysis (total lung volume) - SVC breathhold at CT scanning $\geq 90\%$ of SVC supine - Least Square Means for change In baseline
14.2.19.2.1.1 to 14.2.19.2.1.2	(EO2) Exploratory analyses: HRCT image analysis (total lung volume) - SVC breathhold at CT scanning $< 90\%$ of SVC supine - raw value at each visit
14.2.19.2.2.1.b to 14.2.19.2.2.2	(EO2) Exploratory analyses: HRCT image analysis (total lung volume) - SVC breathhold at CT scanning $< 90\%$ of SVC supine - change from baseline
14.2.19.2.3.1.a to 14.2.19.2.3.2.a	(EO2) Exploratory analyses: HRCT image analysis (total lung volume) - SVC breathhold at CT scanning $< 90\%$ of SVC supine - Anova table
14.2.19.2.3.1.b to 14.2.19.2.3.2.b	(EO2) Exploratory analyses: HRCT image analysis (total lung volume) - SVC breathhold at CT scanning $< 90\%$ of SVC supine - Model parameter estimates
14.2.19.2.3.1.c to 14.2.19.2.3.2.c	(EO2) Exploratory analyses: HRCT image analysis (total lung volume) - SVC breathhold at CT scanning $< 90\%$ of SVC supine - Least Square Means for change I nbaseline
14.2.20.1.1 to 14.2.20.1.2	(EO2) Exploratory Efficacy Analysis: King's Brief Interstitial Lung Disease Questionnaire (K-BILD) - raw values at each visit
14.2.20.2.1 to 14.2.20.2.2	(EO2) Exploratory Efficacy Analysis: King's Brief Interstitial Lung Disease Questionnaire (K-BILD) - change from baseline to each visit
14.2.20.3.1.a to 14.2.20.3.2.a	(EO2) Exploratory Efficacy Analysis: King's Brief Interstitial Lung Disease Questionnaire (K-BILD) - Anova table
14.2.20.3.1.b to 14.2.20.3.2.b	(EO2) Exploratory Efficacy Analysis: King's Brief Interstitial Lung Disease Questionnaire (K-BILD) - Model parameter estimates
14.2.20.3.1.c to 14.2.20.3.2.c	(EO2) Exploratory Efficacy Analysis: King's Brief Interstitial Lung Disease Questionnaire (K-BILD) - Least Square Means by stratum at each visit
14.2.20.3.1.d to 14.2.20.3.2.d	(EO2) Exploratory Efficacy Analysis: King's Brief Interstitial Lung Disease Questionnaire (K-BILD) - Least Square Means for change from baseline at each visit
14.2.21.1.1 to 14.2.21.1.2	(EO2) Exploratory Efficacy Analysis: Leicester Cough Questionnaire (LCQ) - raw values at each visit
14.2.21.2.1 to 14.2.21.2.2	(EO2) Exploratory Efficacy Analysis: Leicester Cough Questionnaire (LCQ) - change from baseline to each visit
14.2.21.3.1.a to 14.2.21.3.2.a	(EO2) Exploratory Efficacy Analysis: Leicester Cough Questionnaire (LCQ) - Least Square Means
14.2.21.3.1.b to 14.2.21.3.2.b	(EO2) Exploratory Efficacy Analysis: Leicester Cough Questionnaire (LCQ) - Anova table
14.2.21.3.1.c to 14.2.21.3.2.c	(EO2) Exploratory Efficacy Analysis: Leicester Cough Questionnaire (LCQ) - Model parameter estimates

14.2.21.4.1 to 14.2.21.4.2	(EO2) Exploratory Efficacy Analysis: Leicester Cough Questionnaire (LCQ) - frequency of patients with changes below or above 1.3 at each visit
14.2.22.1.1 to 14.2.22.1.2	(EO2) Exploratory Efficacy Analysis: anti-Pentraxin-2 antibodies - raw values at each visit
14.2.22.2.1 to 14.2.22.2.2	(EO2) Exploratory Efficacy Analysis: anti-Pentraxin-2 antibodies - change from baseline to each visit
14.2.23.1.1 to 14.2.23.1.2	(EO3) Exploratory Efficacy Analysis: Use of quantitative imaging in IPF - Baseline correlations
14.2.23.2.1 to 14.2.23.2.2	(EO3) Exploratory Efficacy Analysis: Use of quantitative imaging in IPF - Correlations with change from baseline to week 28 in FVC [%predicted]
14.2.23.3.1 to 14.2.23.3.2	(EO3) Exploratory Efficacy Analysis: Use of quantitative imaging in IPF - Correlations with change from baseline to week 28 in DLCO
14.2.23.4.1 to 14.2.23.4.2	(EO3) Exploratory Efficacy Analysis: Impact of respiratory effort on HRCT quantitative imaging
14.2.24.1.to 14.2.24.2	(EO4) Exploratory analyses: Biomarkers
14.2.25.1.1 to 14.2.25.1.2	(EOA) Additional Exploratory analyses: Influence of ADA on FVC[%predicted] - model selection
14.2.25.2.1 to 14.2.25.2.2	(EOA) Additional Exploratory analyses: Influence of ADA on FVC[%predicted] - model parameter estimates
14.2.26.1 to 14.2.26.2	(EOA) Additional Exploratory analyses: PK/PD relationship
14.2.27.1 to 14.2.27.2	(EOA) Additional Exploratory analyses: Relationship between Pentraxin-2 levels and ADA
14.2.28.1.1 to 14.2.28.1.2	(EOA) Additional Exploratory analyses: Acute exacerbations
14.2.28.2.1 to 14.2.28.2.2	(EOA) Additional Exploratory analyses: Acute exacerbations - Descriptive statistics
14.2.29.1.1.1 to 14.2.29.1.1.2	(EOA) Additional Exploratory Efficacy Analysis: Forced Vital Capacity (% predicted FVC) - raw value at each visit - Nintedanib
14.2.29.1.2.1 to 14.2.29.1.2.2	(EOA) Additional Exploratory Efficacy Analysis: Forced Vital Capacity (% predicted FVC) - change from baseline - Nintedanib
14.2.29.1.3.1.a to 14.2.29.1.3.2.a	(EOA) Additional Exploratory Efficacy Analysis: Forced Vital Capacity (% predicted FVC) - Separately for each stratum - Anova table - Nintedanib
14.2.29.1.3.1.b to 14.2.29.1.3.2.b	(EOA) Additional Exploratory Efficacy Analysis: Forced Vital Capacity (% predicted FVC) - Separately for each stratum - Model parameter estimates - Nintedanib
14.2.29.1.3.1.c to 14.2.29.1.3.2.c	(EOA) Additional Exploratory Efficacy Analysis: Forced Vital Capacity (% predicted FVC) - Separately for each stratum - Least Square Means at each visit - Nintedanib
14.2.29.1.3.1.d to 14.2.29.1.3.2.d	(EOA) Additional Exploratory Efficacy Analysis: Forced Vital Capacity (% predicted FVC) - Separately for each stratum - Least Square Means for change from baseline at each visit - Nintedanib
14.2.29.2.1.1 to 14.2.29.2.1.2	(EOA) Additional Exploratory Efficacy Analysis: Forced Vital Capacity (% predicted FVC) - raw value at each visit - Pirfenidone

14.2.29.2.2.1 to 14.2.29.2.2.2	(EOA) Additional Exploratory Efficacy Analysis: Forced Vital Capacity (% predicted FVC) - change from baseline - Pirfenidone
14.2.29.2.3.1.a to 14.2.29.2.3.2.a	(EOA) Additional Exploratory Efficacy Analysis: Forced Vital Capacity (% predicted FVC) - Separately for each stratum - Anova table - Pirfenidone
14.2.29.2.3.1.b to 14.2.29.2.3.2.b	(EOA) Additional Exploratory Efficacy Analysis: Forced Vital Capacity (% predicted FVC) - Separately for each stratum - Model parameter estimates - Pirfenidone
14.2.29.2.3.1.c to 14.2.29.2.3.2.c	(EOA) Additional Exploratory Efficacy Analysis: Forced Vital Capacity (% predicted FVC) - Separately for each stratum - Least Square Means at each visit - Pirfenidone
14.2.29.2.3.1.d to 14.2.29.2.3.2.d	(EOA) Additional Exploratory Efficacy Analysis: Forced Vital Capacity (% predicted FVC) - Separately for each stratum - Least Square Means for change from baseline at each visit - Pirfenidone
14.2.30.1.1 to 14.2.30.1.2	(EOA) Additional Exploratory Efficacy Analysis: Historic Forced Vital Capacity (% predicted FVC) – Model parameter estimates
14.2.30.2.1 to 14.2.30.2.2	(EOA) Additional Exploratory Efficacy Analysis: Historic Forced Vital Capacity (ml) – Model parameter estimates
n°	SAFETY RESULTS
14.3.1	Extent of exposure
14.3.2.1 to 14.3.2.3	Pentraxin-2 levels over time
14.3.3	Summary of Adverse Events
14.3.4.1	Treatment Emergent Adverse Events (TEAEs) by System Organ Class (SOC) and Preferred Term (PT)
14.3.4.2	Frequent Treatment Emergent Adverse Events (TEAEs) (>5% Overall) by System Organ Class (SOC) and Preferred Term (PT)
14.3.4.3	Possibly or Probably Related Treatment Emergent Adverse Events (TEAEs) by System Organ Class (SOC) and Preferred Term (PT)
14.3.4.4	Treatment Emergent Adverse Events (TEAEs) by System Organ Class (SOC), Preferred Term (PT) and Intensity
14.3.4.5	Treatment Emergent Adverse Events (TEAEs) Leading to Permanent Study Drug Discontinuation by System Organ Class (SOC) and Preferred Term (PT)
14.3.4.6	All TEAEs leading to permanent study discontinuation by SOC and PT
14.3.5.1	Serious Treatment Emergent Adverse Events (TEAEs) by System Organ Class (SOC) and Preferred Term (PT)
14.3.5.2	Possibly or Probably Related Serious Treatment Emergent Adverse Events (TEAEs) by System Organ Class (SOC) and Preferred Term (PT)
14.3.5.3	Serious Treatment Emergent Adverse Events (TEAEs) by System Organ Class (SOC), Preferred Term (PT) and Intensity
14.3.5.4	Serious Treatment Emergent Adverse Events (TEAEs) Leading to Permanent Study Drug Discontinuation by System Organ Class (SOC) and Preferred Term (PT)
14.3.5.5	All TESAEs leading to permanent study discontinuation by SOC and PT
14.3.5.6	Deaths
14.3.6.1	Respiratory Decline Treatment Emergent Adverse Events (TEAEs) by System Organ Class (SOC) and Preferred Term (PT)

14.3.6.2	Respiratory Decline Treatment Emergent Adverse Events (TEAEs) by System Organ Class (SOC), Preferred Term (PT) and Intensity
14.3.6.3	Respiratory Decline Treatment Emergent Adverse Events (TEAEs) by System Organ Class (SOC), Preferred Term (PT) and Seriousness
14.3.7.1.1	Infusion Related Reaction Treatment Emergent Adverse Events (TEAEs) by System Organ Class (SOC) and Preferred Term (PT)
14.3.7.1.2	Infusion Related Reaction Treatment Emergent Adverse Events (TEAEs) by System Organ Class (SOC), Preferred Term (PT) and Intensity
14.3.7.1.3	Infusion Related Reaction Treatment Emergent Adverse Events (TEAEs) by System Organ Class (SOC), Preferred Term (PT) and Seriousness
14.3.7.2.1	Infusion Related Reactions by Preferred Term (PT) and presence/absence of ADA
14.3.7.2.2	Infusion Related Reactions by Preferred Term (PT), intensity and presence/absence of ADA
14.3.7.2.3	Infusion Related Reactions by Preferred Term (PT), seriousness and presence/absence of ADA
14.3.8.1.1	Laboratory Tests - Hematology - Descriptive statistics for raw values
14.3.8.1.2	Laboratory Tests - Hematology - Descriptive statistics for change from baseline
14.3.8.2	Laboratory Tests - Hematology - Qualitative
14.3.8.3	Laboratory Tests - Hematology - Shift tables
14.3.9.1.1	Laboratory Tests - Chemistry - Descriptive statistics for raw values
14.3.9.1.2	Laboratory Tests - Chemistry - Descriptive statistics for change from baseline
14.3.9.2	Laboratory Tests - Chemistry - Qualitative
14.3.9.3	Laboratory Tests - Chemistry - Shift tables
14.3.10.1.1	Laboratory Tests - Coagulation - Descriptive statistics for raw values
14.3.10.1.2	Laboratory Tests - Coagulation - Descriptive statistics for change from baseline
14.3.10.2	Laboratory Tests - Coagulation - Qualitative
14.3.10.3	Laboratory Tests - Coagulation - Shift tables
14.3.11	Physical Examination
14.3.12.1	Vital signs - Descriptive statistics for raw values
14.3.12.2	Vital signs - Descriptive statistics for change from baseline
14.3.12.3	Vital signs - Descriptive statistics for normal/abnormal values
14.3.12.4	Vital signs - Shift tables
14.3.13.1	Concomitant medication at baseline
14.3.13.2	Concomitant medication started after baseline
14.3.13.3	Concomitant medications - Use of nintedanib and pirfenidone at baseline
14.3.13.4	Concomitant medications - Use of nintedanib and pirfenidone started after baseline

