1.3.2. Retrospective Quantitative Imaging Analysis of PRM-151 Data

Imbio Lung Texture Analysis was applied retrospectively to HRCT obtained at screening and Day 57 in Study PRM151f-12GL. Limitations of retrospective analysis included, the fact that the datasets contained reconstructed images of variable slice thickness, reconstruction kernel and temporal correlation with the physiologic tests were available. In particular, the slice thicknesses for some CT scans were ≥ 5 mm for some subjects and volumetric HRCT was not available at both time points for any of the subjects. In addition, validation of the inspiratory volume was not prospectively controlled, with full inspiration of the subjects during the scan assumed but not specifically coached by the performing technologist or measured by spirometry. Lung Texture Analysis results were reported as change from screening to Day 57 in % total lung volume occupied by any of the ILA texture types (ground glass, reticular or honeycombing) and non-ILA (normal parenchyma or mild LAA). Areas of moderate or severe LAA that are characteristic of emphysema were excluded from the analysis. Quantitative imaging data was analyzed in 16 subjects who had ≤ 36 days between screening CT and Day 1 PFTs. There was a strong negative correlation between baseline FVC % predicted and percent of lung volume identified as ILA by Imbio Lung Texture Analysis software. Non-ILA lung decreased in all placebo subjects and was stable or increased in 5 PRM-151 treated subjects, all of whom had stable or increased FVC % predicted. There was no clear correlation between the magnitude of change in FVC% predicted and %Non-ILA, possibly due the limitations inherent to retrospective analysis of the HRCT data. The analysis was confounded in 4 subjects by apparent poor inspiratory effort and resultant

atelectasis and increase in overall lung density for the HRCT series that should have been performed at TLC on the Day 57.

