5.2.5.2 Secondary efficacy analyses

For all secondary efficacy endpoints, the analyses will be based on observed data only *i.e.*, no data will be imputed. All the following analyses will be performed on both the ATS and the PP analysis data set.

SO1: *To determine the effect size of PRM-151 relative to placebo in change from Baseline to Week 28 in normal lung parenchyma (normal + mild LAA) and interstitial lung abnormalities (ILA) as quantified on high-resolution CT (HRCT) imaging analysis, pooling subjects on a stable dose of pirfenidone or nintedanib with subjects not on other treatment for IPF.*

HRCT is performed at baseline and W28. Descriptive statistics will be computed by treatment group for baseline, week 28 and change from baseline to Week 28 in total lung volume and volume (in ml and % of total lung volume) of parenchyma features representative of normal lung (normal + mild LAA) and representative of interstitial lung abnormalities (ILA) as quantified by HRCT imaging (see section 8, Statistical table 14.2.6.1.1 and 14.2.6.2.2). A model similar to that of the primary analysis (see section 5.2.5.1) will be used to compare the two groups (Statistical tables 14.2.6.3.1 to 14.2.6.3.2, Figure 14.2.4.1 to 14.2.4.2). Individual's measurement of total lung volume and volume of parenchymal features quantified by HRCT imaging will be reported in Listing 16.2.6.3.

SO2: *To determine the effect size of PRM-151 relative to placebo in change from Baseline to Week 28 in mean FVC% predicted, separately in subjects on a stable dose of pirfenidone or nintedanib and in subjects not on other treatments for IPF.*

The same model as the one for the primary analysis (see section 5.2.5.1) will be used for each subgroup (Statistical table 14.2.7.1.1 to 14.2.7.2.2, Figure 14.2.5.1.1 to 14.2.5.2.2). All measurements of FVC [% predicted] will be reported in Listing 16.2.6.1.1.

SO3: *To determine the effect size of PRM-151 relative to placebo in change from Baseline to Week 28 in normal lung (defined as normal + mild LAA) parenchyma and interstitial lung abnormalities (ILA) as quantified on HRCT imaging analysis, separately in subjects on a stable dose of pirfenidone or nintedanib and in subjects not on other treatments for IPF.*

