SO7: To determine the effect size of PRM-151 relative to placebo on 6-minute walking distance

The same descriptive statistics and analysis model as those of the primary analysis (see section 5.2.5.1) will be used (Statistical tables 14.2.10.1.1 to 14.2.10.3.2, Figure 14.2.7.1 to 14.2.7.2). All results of the 6-minute walk test will be reported in Listing 16.2.6.2.

SO8: To determine the effect size of PRM-151 relative to placebo on DLCO.

The same descriptive statistics and analysis model as those of the primary analysis (see section 5.2.5.1) will be used (Statistical tables 14.2.11.1.1 to 14.2.11.3.2, Figure 14.2.8.1 to 14.2.8.2). All DLCO measurements will be reported in Listing 16.2.6.1.2.

SO9: To determine the correlation between change in FVC [% predicted] and total lung volume and volume of ILA on HRCT from Baseline to Week 28

Correlation between change from baseline in FVC[% predicted] and (i) total lung volume (Statistical table 14.2.12.1.1 and 14.2.12.1.2, Figures 14.2.9.1.1 and 14.2.9.1.2) and (ii) volume of ILA on HRCT will be produced along with the corresponding scatter plots (Statistical table 14.2.12.2.1 and 14.2.12.2.2, Figures 14.2.9.2.1 and 14.2.9.2.2).

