Change in Patient Reported Outcomes will be assessed based on the King's Brief Interstitial Lung Disease Questionnaire (K-BILD) and Leicester Cough Questionnaire (LCQ). Descriptive statistics for raw values and change from Baseline to each visit in total score of both questionnaire will be computed by treatment group. Differences between treatment groups in change from baseline to week 28 for total score of each questionnaire will be tested using a similar approach to the one used for the primary analysis (see section 5.2.5.1). These analysis will be performed on both the ATS and the PP data sets (Statistical tables 14.2.20.1.1 to 14.2.20.3.2 and 14.2.21.1.1 to 14.2.21.3.2, Figures 14.2.17.1 to 14.2.17.2 and 14.2.18.1 to 14.2.18.2). All results of K-BILD and LCQ will be reported in Listings 16.2.6.4.1 to 14.2.6.4.2.2 and 16.2.6.5.1 to 16.2.6.5.2.2.

For the LCQ, in addition to the above approach, frequency of patients with changes below or above 1.3 (identified as the minimal important difference) will be tabulated by treatment groups at week 4, 8, 12, 16, 20, 24 and 28 (Statistical table 14.2.21.4.1 and 14.2.21.4.2).

Descriptive statistics for raw values at each visit and change from baseline to each visit in anti-Pentraxin-2 antibodies measurements will be computed by treatment group. This analysis will be performed on both the ATS and the PP dataset (Statistical 14.2.22.1.1 to 14.2.22.2.2). Individual measurements of anti-pentraxin-2 antibodies will be reported in Listing 16.2.6.8.

EO3: To assess the use of quantitative imaging in IPF

The correlation between baseline FVC [% predicted], DLCO (corrected for Hb, [% predicted]), TLC by nitrogen washout, PROs and 6MWD and total lung volume and volume of parenchymal features on HRCT (in ml and % of total lung volume) representative of ILA by quantitative imaging, as well as change from Baseline to Week 28 in FVC [% predicted], DLCO (corrected for Hb, [% predicted]), TLC by nitrogen washout, PROs and 6MWD and change from Baseline to Week 28 in total lung volume and volume of parenchymal features on HRCT (in ml and % of total lung volume) representative of ILA will be computed. This analysis will be performed on both the ATS and the PP dataset (Statistical tables 14.2.23.1.1 to 14.2.23.1.2).

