For all categories of lung features (including PVV) the correlation between (i) change from baseline to week 28 in volume of a given lung feature (both in ml as well as in % of total lung volume) and (ii) change from baseline to week 28 in FVC [% predicted] will be computed. This analysis will be performed on both the ATS and the PP dataset (Statistical tables 14.2.23.2.1 to 14.2.23.2.2).

For all categories of lung features (including PVV) the correlation between (i) change from baseline to week 28 in volume of a given lung feature (both in ml as well as in % of total lung volume) and (ii) change from baseline to week 28 in DLCO will be computed. This analysis will be performed on both the ATS and the PP datasets (Statistical table 14.2.23.3.1 to 14.2.23.3.2).

The impact of inspiratory effort on results of HRCT quantitative imaging will be assessed by (Statistical table 14.2.23.4.1 to 14.2.23.4.2, Figure 14.2.19.1 to 14.2.19.2):

1. Calculating the proportion of patients performing spirometry guided HRCT with a SVC breathhold at CT scanning $\geq 90\%$ of SVC supine at baseline and at week 28
2. The correlation of SVC breathhold at CT scanning and SVC supine at baseline and at week 28
3. The correlation between (i) baseline Total lung volume by quantitative imaging and (ii) baseline TLC by nitrogen washout, separately for patients with SVC breathhold at CT scanning $\geq 90\%$ of SVC supine, and for patients with SVC $< 90\%$ or not receiving spirometry-guided HRCT.

EO4: To assess the impact of PRM-151, disease pathogenesis and disease progression on exploratory serum, cellular and genetic biomarkers

To assess the impact of PRM-151 on exploratory biomarkers, descriptive statistics for change from baseline to week 28 in biomarkers will be computed by treatment group and by baseline genetic status (MUC5B and TLR polymorphism separately). These analyses will be performed on both the ATS and the PP dataset (Statistical table 14.2.24.1 and 14.2.24.2). Individual biomarker values will be reported in Listing 16.2.6.6. All or part of these analyses may be provided at a later stage than the rest of the analyses described in the SAP, might the corresponding data not be available at the time of the database lock. It is currently anticipated that baseline genetic status will be available, but biomarkers will not.

Additional exploratory analysis: ADA vs. FVC [% predicted]

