14.2.11.3.1b to 14.2.11.3.2b	(SO8) Secondary Efficacy Analysis: DLCO - Model parameter estimates
14.2.11.3.1c to 14.2.11.3.2c	(SO8) Secondary Efficacy Analysis: DLCO - Least Square Means by stratum for change from baseline
14.2.12.1.1 to 14.2.12.1.2	(SO9) Secondary Efficacy Analysis: Correlation between Forced Vital Capacity (% predicted FVC) and total lung volume
14.2.12.2.1 to 14.2.12.2.2	(SO9) Secondary Efficacy Analysis: Correlation between Forced Vital Capacity (% predicted FVC) and volume of ILA on HRCT
14.2.13.1.a to 14.2.13.2.a	(EO1) Exploratory analyses: FV [%predicted] - Random Slope Analysis - Anova table
14.2.13.1.b to 14.2.13.2.b	(EO1) Exploratory analyses: FV [%predicted] - Random Slope Analysis- Model parameter estimates

14.2.13.1.c to 14.2.13.2.c	(EO1) Exploratory analyses: FV [%predicted] - Random Slope Analysis- Least Square Means by stratum at each visit
14.2.13.1.d to 14.2.13.2.d	(EO1) Exploratory analyses: FV [%predicted] - Random Slope Analysis- Least Square Means for change from baseline at each visit
14.2.14.1.1.a to 14.2.14.1.2.a	(EO1) Exploratory analyses: FV [%predicted] - Random Slope Analysis Separately for each stratum - Anova table - No Background Therapy
14.2.14.1.1.b to 14.2.14.1.2.b	(EO1) Exploratory analyses: FV [%predicted] - Random Slope Analysis Separately for each stratum - Model parameter estimates - No Background Therapy
14.2.14.1.1.c to 14.2.14.1.2.c	(EO1) Exploratory analyses: FV [%predicted] - Random Slope Analysis Separately for each stratum - Least Square Means at each visit - No Background Therapy
14.2.14.1.1.d to 14.2.14.1.2.d	(EO1) Exploratory analyses: FV [%predicted] - Random Slope Analysis Separately for each stratum - Least Square Means for change from baseline at each visit - No Background Therapy
14.2.14.2.1.a to 14.2.14.2.2.a	(EO1) Exploratory analyses: FV [%predicted] - Random Slope Analysis Separately for each stratum - Anova table - Pirfenidone or Nintedanib
14.2.14.2.1.b to 14.2.14.2.2.b	(EO1) Exploratory analyses: FV [%predicted] - Random Slope Analysis Separately for each stratum - Model parameter estimates - Pirfenidone or Nintedanib
14.2.14.2.1.c to 14.2.14.2.2.c	(EO1) Exploratory analyses: FV [%predicted] - Random Slope Analysis Separately for each stratum - Least Square Means at each visit- Pirfenidone or Nintedanib

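### The SAP specifies no by-arm or treatment-adjusted correlation between on-study FVC and CT changes (SO9, EO3), so a drug effect on both measures would modestly distort the single pooled coefficient

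*SAP*

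**What the plan says.** Protocol 3.2 and SAP 4.1.2 list, as a secondary endpoint, the correlation between change in FVC % predicted and change in total lung volume and ILA volume on HRCT.

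- **SO9 (SAP 5.2.5.2).** The analysis is "Correlation between change from baseline in FVC[% predicted] and (i) total lung volume", and (ii) "volume of ILA on HRCT will be produced along with the corresponding scatter plots". The introduction to that section adds: "All the following analyses will be performed on both the ATS and the PP analysis data set".
- **EO3 (SAP 5.2.5.3).** Changes in FVC, DLCO, TLC, patient-reported outcomes and walk distance are correlated with changes in lung volume and features "representative of ILA will be computed. This analysis will be performed on both the ATS and the PP dataset". For each lung feature, the correlation of its change with "change from baseline to week 28 in FVC [% predicted] will be computed", and the same is planned for DLCO.
- **Table list (SAP 9.1).** Tables 14.2.12.1 and 14.2.12.2 (the latter titled "Correlation between Forced Vital Capacity (% predicted FVC) and volume of ILA on HRCT") each come as a pair, as do the 14.2.23 tables. The pairs match the two analysis sets, so no by-arm tables are listed.
- **Adjustment rule (SAP 5.3.1).** It covers ANOVA comparisons and linear mixed models. It does not mention correlations.

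Where the SAP wants a split it says so: the SO1 descriptive statistics are by treatment group, and one EO3 baseline correlation is split by breath-hold quality. None of the correlations of changes is split or adjusted.

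**The concern.** These analyses ask whether patients whose CT picture changes more also have a larger change in lung function. A coefficient computed over both arms answers that only if treatment does not shift both measures. If it does, the treated patients sit together at one end of the scatter plot and the placebo patients at the other. The pooled coefficient then moves away from its within-arm value even when the two changes are unrelated within each arm. The plan expects an FVC shift and sets out to estimate a CT shift (SO1), so the distortion would appear in the trial that succeeds on both. At stake is the reading of one secondary and several exploratory results; the primary analysis is not touched.

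**Working it through.** **Inputs from Protocol 8.1:** 2:1 allocation; expected FVC change of −1.5 (on pirfenidone or nintedanib) and −3 (no other treatment) without PRM-151, and 0.75 on PRM-151; SD 5; strata 75:25; 102 evaluable patients; two-sided alpha 0.10. SAP 5.1.2 sets 90% intervals for secondary and exploratory analyses.

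**Assumptions:** The documents give no drug effect on CT, so a range of d₂ in within-arm SD is used. The SAP does not name the coefficient; Pearson is assumed.

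**Step 1, the plan's own figure.** Weighted difference = 0.75 × (0.75 + 1.5) + 0.25 × (0.75 + 3) = 2.625. At SD 5, alpha 0.10 two-sided, power 80% and 2:1, this needs 34 placebo and 68 PRM-151, total 102. The stated size is reproduced (power 80.4%). The standardised FVC effect is d₁ = 2.625 / 5 = 0.525.

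**Step 2, pooled correlation.** With within-arm correlation ρ and p(1 − p) = (2/3)(1/3) = 2/9:

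r = (ρ + (2/9)d₁d₂) / √[(1 + (2/9)d₁²)(1 + (2/9)d₂²)]

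Example with ρ = 0 and d₂ = 0.5: 0.0583 / √(1.0613 × 1.0556) = 0.055.

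**Step 3, chance that the 90% interval excludes zero.** With z = atanh(r) × √99, the chance is 1 − Φ(1.645 − z) + Φ(−1.645 − z). The interval excludes zero once the observed |r| passes about 0.164.

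| CT effect (SD, assumed) | Pooled r, ρ = 0 | 90% interval excludes 0 | Pooled r, ρ = 0.30 |
|---|---|---|---|
| 0 | 0.00 | 10% | 0.29 |
| 0.25 | 0.03 | 11% | 0.32 |
| 0.5 | 0.055 | 15% | 0.34 |
| 1.0 | 0.10 | 27% | 0.37 |
| 1.5 | 0.14 | 40% | 0.38 |
| 2.0 | 0.16 | 50% | 0.38 |

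Values are absolute for effects in the favourable direction; for ILA, the induced r is negative if the drug lowers ILA.

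**Step 4, ceiling.** As d₂ grows without limit, r tends to √(2/9) × 0.525 / √1.06125 = 0.24. This ceiling belongs to the planned FVC effect. If both effects were 1.0 SD, r would be 0.18 and the interval would exclude zero in 57% of trials.

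**Step 5, simulation.** In 20,000 simulated trials (68/34, two strata, no within-arm correlation, CT effect by treatment only), CT effects of 0.525 and 1.0 SD gave pooled r of 0.057 and 0.102, with rejection in 15.8% and 27%. The partial correlation given treatment averaged 0.00 and rejected in 10.1% to 10.3% of trials. When the CT means also followed the planned FVC stratum pattern, adjusting for treatment alone left an average of 0.005 to 0.02, and for treatment plus stratum 0.003 to 0.014. Rejection stayed at 9.9% to 10.4%.

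**The case against.** **The endpoint is defined as the overall correlation.** Protocol 3.2 does not ask for an association net of treatment, and movement of both measures caused by the drug is arguably part of what it describes. This stands. It is a reason to keep the overall coefficient and add the adjusted one, not to replace it.

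**Pooling is inferred.** The SAP never says that the arms are combined. This also stands: the supportable statement is that no arm handling is specified. The paired tables and the explicit splits elsewhere still make pooling the natural reading.

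**Exact zero is an extreme case.** Protocol 1.3.1 reports that these CT parameters correlate with FVC, and 1.3.2 reports a strong baseline correlation. Those are not correlations of on-study changes, but they make a zero within-arm value the least favourable assumption. The percentages apply to that case only. The caution in SAP 5.1.2 concerns multiple testing and does not correct a shifted coefficient.

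Three stronger readings are tempting, and the documents do not support them:

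- *That the pooled coefficient would pass as validation of the imaging endpoint.* An r of 0.14 is about 2% shared variance (0.14² = 0.02), too small for that.
- *That the earlier IPF study shows the effect.* Protocol 1.3.2 says "Non-ILA lung decreased in all placebo subjects and was stable or increased in 5 PRM-151 treated subjects". Of the 16 analysed, at most 6 were placebo (Table 1-1), so at least 10 were treated and only 5 of these were stable or increased. The arms did not cleanly separate. The report of no clear correlation in the size of changes is not stated to be within arms, and the section offers scan limitations as a possible explanation.
- *That a correlation is created where none exists within patients.* Each patient contributes one change per measure, so every coefficient here is between patients. The relevant contrast is within arms versus pooled.

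**Conclusion.** The concern holds as a gap in specification with a modest, conditional effect. It does not point to a strong false correlation; the harm is an interval that excludes zero more often than its nominal 10%, together with some inflation or slight dilution of a real association. With a true 0.30 within arms, the pooled value reads 0.34 to 0.37 for CT effects of about 0.5 to 1 SD, and 0.29 if the drug does not move CT.

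The sizes rest on the planned FVC effect, 102 complete pairs, equal within-arm variances, Pearson correlation and an assumed CT effect. Fewer complete pairs would lower the exclusion rates but not the induced r. For EO3 pairs that do not involve FVC % predicted the mechanism is the same, but the documents give no planned effects from which to size it. Treatment is the adjustment that matters; stratum adds little.

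**What to change.** In SAP 5.2.5.2 (SO9) and 5.2.5.3 (EO3), before unblinding, state for every change-versus-change correlation that:

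1. the overall correlation defined in the protocol is reported, and beside it a partial correlation adjusted for treatment arm and stratum, with its 90% interval (stratum is included for consistency with SAP 5.3.1);
2. any statement that CT change tracks FVC change rests on the adjusted coefficient;
3. the arms are marked on the scatter plots.

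This covers tables 14.2.12, 14.2.23.2 and 14.2.23.3. It also covers the change correlations that 5.2.5.3 places under 14.2.23.1, although SAP 9.1 titles that table as baseline correlations only. Baseline correlations need no change.

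The cost is one extra coefficient per pair and two degrees of freedom: the standard error on the Fisher scale goes from 1/√99 = 0.1005 to 1/√97 = 0.1015. No new data are needed.

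Fixing this before unblinding avoids a later choice between the two coefficients that depends on the results.
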